This is a post-market, single-arm, prospective clinical study to evaluate fusion status and patient reported outcomes using the Spira-C titanium interbody cage for degenerative disc disease where single-level ACDF surgery is indicated. The treatment group will consist of 40 subjects treated with the Spira™-C Interbody Device at one level. Patients with a diagnosis of cervical degenerative disc disease and/or spinal stenosis, radiculopathy or myelopathy and planning to undergo a 1-level ACDF surgery between C3-C7 will be screened. If the subject meets all of the inclusion criteria and none of the exclusion criteria, the patient will be approached regarding study participation by the surgeon or study coordinator. If the subject wishes to participate, the study coordinator will initiate the consent process. Once the consent process has been completed and the subject has signed an IRB approved informed consent form the medical history, cervical spine examination (motor/sensory), and baseline subject questionnaires (VAS, NDI, SF-36, and EAT-10) will be collected. Once the ACDF surgery has taken place as planned; data will be regarding the surgery performed, operative time, bone graft used, plate and screw fixation system used,

length of stay, and adverse events or complications related to the procedure, device, or cervical spine.

Subjects will be followed up postoperatively at 6-weeks, 3-months, 6-months, and 12-months as per standard of care, at the private practice or clinic. During these visits, subjects will complete the questionnaires, cervical spine (motor/sensory) examination completed by the investigator, and cervical spine x-rays done per standard of care. Adverse events related to the device and/or procedure and/or cervical spine will be assessed at each visit.

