1. Any prior history of cervical fusion
2. Requires cervical fusion of more than one level
3. Acute cervical spine trauma requiring immediate intervention
4. BMI > 40
5. Active systemic bacterial or fungal infection or infection at the operative site
6. History of vertebral fracture or osteoporotic fracture
7. Current treatment with chemotherapy, radiation, immunosuppression or chronic steroid therapy
8. History of osteoporosis, osteopenia, or osteomalacia that would contraindicate spinal surgery
9. Psychological or physical condition in the opinion of the investigator that would interfere with completing study participation including completion of patient reported outcomes
10. History of neurological condition in the opinion of the investigator that may affect cervical spine function and pain assessments
11. Subjects with a history of cancer must be disease free for at least 3 years; with the exception of squamous cell skin carcinoma
12. Pregnant, or plans on becoming pregnant
13. History of allergy to titanium

Intervention

The intervention will consist of 40 patients undergoing an anterior cervical discectomy and fusion surgery where the Spira™-C Open Matrix Cervical Interbody cage with autograft and allograft will be utilized for interbody fusion at a single-level between C3-C7.

Statistical Analysis

The primary objective of this pilot study is to evaluate fusion status using the Spira™-C titanium interbody device at the 12-months postoperative time point. Results obtained in this study will be compared to historical data based on literature review. Based on previous literature review, a sample size of 40 patients was determined to be adequate for this study. The Wilson Score method was used to calculate two-sided confidence intervals for a single proportion (fusion rate) from .70 to 1.00. A sample size of 40 produces a two-sided 95% confidence interval with a width equal to 0.274 when the sample proportion is 0.70 and 0.088 when the sample proportion is 1.00. The intervals may be wider based on dropout rate at the 12-month endpoint. Due to the pilot nature of this study, the dropout rate will help to provide an estimate for similar future studies.

Data and Safety Monitoring

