The PI and study team (including sub-investigators, clinical research manager) will be responsible for data and safety monitoring. All adverse events will be reviewed to determine relatedness to the product and reported to sponsor as necessary (if related to product and unanticipated according to risk profile). The data will be reviewed for maintenance of confidentiality and integrity as well as the data collection process. The data and safety review will take place every six months from the date of the first patient enrolled into the study or after ten patients have been enrolled whichever comes first.

Adverse Events

Relevant adverse events (those related to the study device, the surgical procedure, or cervical spine) or complications will be recorded in this study; including revision surgery at the index level, pseudoarthrosis, subsidence, migration, and failure or loosening of the device. Subsidence, migration, or loosening of the device that result in non-union or pseudoarthrosis and/or clinically significant neurological symptomology will be considered a device failure and reported as an adverse event. Any unanticipated serious adverse events related to the device will be reported to the IRB as well as the manufacturer. Per Medical Device Reporting (MDR) regulation (21 CFR 803), manufacturers and facilities are required to report to the FDA when it is known that any of their devices have caused or contributed to a death or serious injury.

Protocol Deviations

The investigators are responsible for documenting all protocol deviations, including an explanation for why the deviation occurred. All protocol deviations will be recorded and submitted to the IRB per policy.

OUTCOMES

Primary Endpoint

- Successful cervical spinal fusion as measured by dynamic (flexion and extension) X-rays and CT scan at 12 months as evidence by the following three criteria: bony bridging, no development of pseudoarthrosis, and no presence of radiolucency

Secondary Endpoints

- Improvement in patient-reported outcomes as measured by VAS (≥ 2 -point improvement), NDI (≥ 15 -point improvement), SF-36 (≥ 15 -point improvement and EAT-10 (score of < 3) from baseline to 12-months.
- No occurrence of adverse events or complications related to the device by month 12; including revision surgery at the index level, subsidence, migration, and failure or loosening of the interbody device. Subsidence, migration, and failure that results

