in non-union or pseudoarthrosis and/or clinically significant neurological symptomology will be considered a device failure and reported as an adverse event.

- No new or worsening neurological (motor and sensory of the cervical spine) deficit as compared to baseline through 12-months.

SUBJECT SCREENING AND ENROLLMENT

Patients scheduled to undergo a primary single-level ACDF surgery between C3-C7 will be approached about potential study participation. If the patient wishes to proceed with study participation, the study coordinator will perform the informed consent process. After the consent process has been completed and study details have been discussed, the subject will be further screened for eligibility and given the subject questionnaires to complete.

Screen Failures

If the subject does not meet all inclusion criteria or meets one of the exclusion criteria after signing consent, then the subject will be considered a screen failure and therefore, not enrolled into the study. The subject will also be considered a screen failure and not enrolled in the study if there is a change in surgical treatment based on the surgeon's observations and best practice intraoperatively.

Withdrawals

A subject who withdraws consent prior to study completion will be removed from the study and no longer followed. The surgery, instrumentation, and bone grafts are FDA approved and cleared and considered standard of care. The subjects may follow-up as needed and per standard of care at their own discretion if they decide to no longer participate in the study. The reasons for voluntary withdrawal or discontinuation of study subjects will be documented. If during the course of the clinical study, a study subject is non-responsive to attempts to schedule follow-up visits, communication methods such as phone calls, emails, mail, or other means as appropriate in an attempt schedule an appointment or determine if the subject has moved, died, or otherwise become lost to follow-up.

Study Synopsis

Sponsor	Camber Spine Technologies [name]
Protocol Version	Version 1.2 Date: 11.01.18
Study Title	A PROSPECTIVE CLINICAL PILOT STUDY OF FUSION RATES USING SPIRA™-C TITANIUM 3D PRINTED INTERBODY DEVICE FOR ANTERIOR CERVICAL DISCECTOMY AND FUSION (ACDF)
Site/ PI	Beaumont Health – Royal Oak (William Beaumont Hospital) Principal Investigator: [name]

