Study Design	Post-market, single-arm, prospective clinical pilot outcomes study
Study Duration	Approximately 3 years (enrollment of first subject to the last follow-up visit)
Enrollment Number	Total: 40 Treatment: 40 Spira™-C Open Matrix Titanium interbody cage (on-label use)
Treatment Arm	40 patients undergoing an anterior cervical discectomy and fusion surgery where the Spira™-C Open Matrix Cervical Interbody cage with autograft and allograft will be utilized on-label for interbody fusion at a single-level between C3-C7.
	Data collected from subjects treated with the Spira™-C Interbody Device will be compared to historical data based on literature review of fusion rates and patient reported outcomes of traditional PEEK interbody cages.
Study Objectives	
Primary Objective:
 
 • To evaluate fusion status using the Spira™-C titanium interbody device for treatment of degenerative disc disease of the cervical spine at a single-level between C3-C7 at 12-months. 
Secondary Objectives:
 
 • To evaluate VAS, ODI, SF-36 and EAT-10 scores postoperatively compared to baseline/preoperative • To evaluate the occurrence of device-related or procedure related adverse events or complications including subsidence and pseudoarthrosis.

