Study Endpoints	
Primary Endpoint:
 
 • Successful cervical spinal fusion as measured by dynamic (flexion and extension) X-rays and CT scan at 12 months and as evidenced by the following three criteria: bony bridging, no development of pseudoarthrosis, and no presence of radiolucency . 
Secondary Endpoints:
 
 • Improvement in patient-reported outcomes as measured by VAS (≥ 2-point improvement), NDI (≥ 15-point improvement), SF-36 (≥ 15-point improvement and EAT-10 (score of < 3) from baseline to 12-months. • No occurrence of adverse events related to the device by month 12; including revision surgery at the index level, subsidence, migration, and failure or loosening of the interbody device. Subsidence, migration, and loosening of the device that result in non-union or pseudoarthrosis and/or clinically significant neurological symptomology will be considered a device failure and reported as an adverse event. • No new or worsening neurological (motor and sensory of the cervical spine) deficit as compared to baseline through 12-months.
Inclusion Criteria	
A subject may be included if the following criteria are met:
 
 1. ≥ 18 years of age and skeletally mature 2. Able to provide consent 3. Undergoing a primary, single-level ACDF between C3-C7 4. Diagnosis of symptomatic degenerative disc disease 5. Neck pain and/or radicular symptoms with a baseline Visual Analog Scale score of ≥ 4 (0-10cm scale) for neck or arm pain 6. Baseline Neck Disability score ≥ 20 7. Attempted at least 6-weeks of conservative non-operative treatment
Exclusion Criteria	
A subject will be excluded if any of the following criteria are met:
 
 1. Any prior cervical fusion surgery 2. Requires cervical fusion of greater than one level 3. Acute cervical spine trauma requiring immediate intervention 4. BMI > 40 5. Active systemic bacterial or fungal infection or infection at operative site 6. History of an osteoporotic fracture and/or vertebral body fracture 7. Current treatment with chemotherapy, radiation, immunosuppression or chronic steroid therapy

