	
 8. History of osteoporosis, osteopenia, or osteomalacia that would contraindicate spinal surgery 9. Psychological or physical condition in the opinion of the investigator that would interfere with study participation, including completion of patient reported outcomes 10. History of neurological condition in the opinion of the investigator that may affect cervical spine function and pain assessments 11. Subjects with a history of cancer must be disease free for at least 3 years; with the exception of squamous cell skin carcinoma 12. Pregnant, or plans on becoming pregnant 13. History of allergy to titanium

Study Schedule of Events
	
All subjects who sign an IRB approved consent form are considered in active screening to determine eligibility. Once a subject is consented, the following visits will take place:
 
Baseline Visit:
 
 • Medical history • Cervical Spine Exam • Demographics • VAS, NDI, SF-36, EAT 10 questionnaires • Cervical spine x-rays AP/lateral, flexion/extension or as done per standard of care 
Surgical Visit (≤ 60 days of baseline visit):
 
 • Surgery performed • Amount of Bone Graft, both local bone autograft/allograft used • Cervical plate and screw fixation system used • Adverse Events/Complications 
6-week Visit (± 2 weeks):
 
 • VAS, NDI, SF-36, EAT 10 • Cervical Spine Exam • Cervical AP/Lateral x-rays • Adverse Events 
3-month Visit (± 3 weeks):
 
 • VAS, NDI, SF-36, EAT 10, patient satisfaction questionnaires • Cervical Spine Exam • Cervical AP/Lateral and flexion/extension x-rays • Adverse Events 
6-month Visit (± 1 month):
 
 • VAS, NDI, SF-36, EAT 10 • Cervical Spine Exam • Cervical AP/Lateral and flexion/extension x-rays • Adverse Events

	
12-month Visit (\pm 2 months):
 
• VAS, NDI, SF-36, EAT 10• Cervical Spine Exam• Cervical AP/Lateral and flexion/extension x-rays• CT scan of the cervical spine without contrast• Adverse Events
--	---

REFERENCES

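### The intraoperative screen-failure rule has no cut-off at attempted Spira-C insertion, so an event in an abandoned attempt may be left out of two secondary safety endpoints

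*Combined protocol and SAP*

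**What the plan says.** **The rule.** Under Subject Screening and Enrollment, Screen Failures, a subject who fails eligibility after consent is a screen failure. A second sentence adds that the subject is also "considered a screen failure and not enrolled in the study if there is a change in surgical treatment", based on what the surgeon observes intraoperatively. The term for a changed treatment is not defined, and no cut-off at device exposure is given there or elsewhere.

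**The endpoints.** Outcomes, Secondary Endpoints asks for "No occurrence of adverse events or complications related to the device by month 12". The Study Synopsis words this as "No occurrence of adverse events related to the device by month 12". A separate secondary endpoint is the absence of a new or worsening motor or sensory deficit, compared with baseline, through 12 months. The matching synopsis objective is "To evaluate the occurrence of device-related or procedure related adverse events or complications including subsidence and pseudoarthrosis". No analysis set is named for any of these.

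**Who is counted.** Study Design describes the treatment group as 40 subjects treated with the device, and the synopsis gives a total enrollment of 40.

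**Collection and reporting.** The Study Schedule of Events starts the visits once a subject has consented, and its Surgical Visit lists "Adverse Events/Complications". Data and Safety Monitoring has all adverse events reviewed for relatedness to the product. The Adverse Events section adds: "Any unanticipated serious adverse events related to the device will be reported to the IRB as well as the manufacturer". Study Design, however, opens its sentence on surgical data with "Once the ACDF surgery has taken place as planned".

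**The concern.** In a device study, exposure starts when insertion is attempted. A rule that removes a subject after that moment can remove the subject because of what happened while the device was being used. If a device-related complication leads the surgeon to abandon Spira-C for another implant or procedure, that is a change of treatment in the ordinary sense of the words, and the subject becomes not enrolled. The complication then has no evident place in the numerator of the device-complication endpoint, and the subject has none in the denominator. The neurological-deficit endpoint would lose the same subject.

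At stake is the reported safety result. For device-related events during an abandoned attempt, the omission can only make the device look better. For an attempt abandoned for an unrelated reason it does not. The protocol asks for documented reasons for withdrawals and discontinuations, but does not ask for the number of intraoperative screen failures or the reasons for them. A reader of the results could not tell which situation applied.

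**Working it through.** **1. The plan's own figures.** Statistical Analysis gives Wilson two-sided 95% interval widths for the fusion rate at n = 40. With z = 1.96, the limits are centre ± half-width, where

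- centre = (p + z²/2n) / (1 + z²/n)
- half-width = z·√(p(1−p)/n + z²/4n²) / (1 + z²/n)

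Results:

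- p = 0.70: 0.5457 to 0.8193, width 0.2736 (stated 0.274)
- p = 1.00: 0.9124 to 1.0000, width 0.0876 (stated 0.088)

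Both reproduce and neither is disputed. The same method is used in step 3.

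**2. Following one subject through the text.** Take a consented, eligible subject in whom Spira-C is attempted, a device-related event occurs, and the surgeon completes the operation with a different device or procedure.

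- *Screen Failures:* the treatment changed intraoperatively, so the subject is not enrolled.
- *Study Design:* the subject is not one of the 40 treated with the device.
- *Secondary Endpoints:* the event is within scope. The items named (revision, subsidence, migration, failure or loosening) concern an implanted cage, but they are introduced as examples. The synopsis objective covers device- and procedure-related events, and the schedule expects events at surgery.
- *Statistical Analysis and Outcomes:* no safety or attempted-treatment set restores the subject.
- *Schedule, Data and Safety Monitoring, Adverse Events:* the event is collected because collection follows consent, is reviewed for relatedness, and is reported if it qualifies. None of these steps places it in an endpoint table.

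The missing cut-off is plain in the text. The omission from the endpoints is an inference from the not-enrolled status, since no analysis set is named. The condition in Study Design that surgery went ahead as planned adds little: the sentence is incomplete, and it does not match the unconditional Surgical Visit entry.

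**3. Possible size.** Only n = 40 and the Wilson method come from the documents. Every event and case count below is an assumption.

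| Events in 40 implanted | Abandoned attempts added | Rate | Wilson 95% CI |
|---|---|---|---|
| 0 | none | 0/40 = 0% | 0 to 8.8% |
| 0 | 1, device-related event | 1/41 = 2.4% | 0.4% to 12.6% |
| 0 | 2, both device-related events | 2/42 = 4.8% | 1.3% to 15.8% |
| 2 | none | 2/40 = 5.0% | 1.4% to 16.5% |
| 2 | 1, device-related event | 3/41 = 7.3% | 2.5% to 19.4% |
| 2 | 1, unrelated reason, no event | 2/41 = 4.9% | 1.3% to 16.1% |

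The second row, worked: z²/2n = 3.8416/82 = 0.0468 and 1 + z²/n = 1.0937, so the centre is (0.0244 + 0.0468)/1.0937 = 0.0651. The half-width is 0.0608, which gives 0.0043 to 0.1260.

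One omitted device-related case therefore moves the rate by about 2.4 points (0% to 2.4%, or 5.0% to 7.3%). One unrelated abandonment moves it 0.1 point the other way. The denominators of 41 and 42 place the abandoned attempts outside the 40 implanted subjects. They compare like with like only for events during surgery, because subjects without the cage have no planned follow-up to month 12.

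**The case against.** **The rule may be meant only for a changed operation.** It directly follows the eligibility sentence, and some intraoperative exclusions are proper, for instance when a second level proves necessary (the exclusion criterion "Requires cervical fusion of more than one level"). That stands, and such exclusions are not criticised here. But the wording is not confined to them. A swap between Spira-C cages is not clearly covered by the rule and is not part of this point.

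**An as-implanted population is coherent** for a single-arm, post-market pilot of a cleared device whose named complications presuppose an implanted cage. That also stands. It is why the implanted set should remain, with the attempted cases shown beside it.

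**No planned conclusion would change.** The plan sets no threshold or test for complications, the historical comparison covers fusion and patient-reported outcomes, and the illustrated intervals overlap heavily. This is correct and limits the weight of the point. It does not remove the selection.

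**Stronger readings that the documents do not support.** A reader might infer that these events go unrecorded or unreported. Surgical-visit collection is tied to consent, relatedness review covers all adverse events, and the Adverse Events section sets out IRB, manufacturer and FDA reporting. A reader might also infer that abandoning the device is itself a complication; nothing in the text makes it one. Nor does the point reach the primary endpoint, because fusion at 12 months is a question about subjects who received the cage.

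**Conclusion.** The point holds as a gap in endpoint tabulation. As written, the screen-failure rule allows a subject to be removed after device exposure because of what happened during that exposure, and nothing in the plan restores the subject. Such a subject may be missing from two secondary endpoints, device complications and neurological deficit. This is not certain, because the analysis set and the meaning of a changed treatment are both left open.

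The size cannot be known from the documents and the number of such cases may be 0. With 40 implanted subjects, one device-related event in an abandoned attempt would be the difference between 0% (upper limit 8.8%) and 2.4% (0.4% to 12.6%). The direction depends on the reason for abandonment: device-related events left out favour the device, and unrelated abandonments left out do not. The as-treated 12-month fusion rate and the planned comparison with historical PEEK data are unaffected.

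**What to change.** 1. For safety tabulation, limit the intraoperative screen-failure exclusion to changes made before Spira-C insertion is attempted.
2. Keep the 40 implanted subjects as the set for fusion, patient-reported outcomes and the month-12 complication rate. Attempted-then-abandoned cases stay outside the 40, so the enrollment total and the primary interval do not change.
3. Beside the month-12 complication rate, report device- or procedure-related adverse events that occur during surgery, including new neurological deficits, in all consented, eligible subjects with attempted insertion. Use the surgical-visit data already planned. A pooled month-12 rate over attempted cases should be avoided: it would mix lengths of follow-up or need extra visits.
4. Report the number and reasons for all intraoperative changes, split by before and after attempted insertion. Do not count abandonment for an unrelated reason as an event.
5. Reconcile the as-planned condition in Study Design with the unconditional Surgical Visit collection in the Study Schedule of Events.

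**Cost.** Wording changes, a case report form line for the timing and reason of any change, and slightly more tabulation. No 12-month follow-up of subjects without the cage is required. The safety result may look slightly less favourable. The Surgical Visit lists no cervical examination, so deficits in abandoned attempts would be counted only where they were recorded as adverse events.

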
OBJECTIVE

The objective of this study is to perform a prospective, single-arm clinical evaluation utilizing the Spira™-C 3-D printed titanium interbody device for treatment of degenerative disc disease and spinal stenosis of the cervical spine to evaluate fusion status and patient reported outcomes. The primary objective is fusion status; this will be measured using dynamic (flexion and extension) X-rays and CT scan at 12 months. Secondary objectives include evaluation of patient reported outcomes, VAS score (pain), NDI (neck disability index; pain and function), SF-36 (quality of life), and EAT-10 (dysphagia). Also, radiographs will be evaluated for the occurrence of device-related adverse events or complications, such as revision surgery at the index level, subsidence, migration, and failure or loosening of the interbody device. Neurological motor and sensory evaluations will be followed for improvement or worsening over the course of the study. Data collected from subjects treated with the Spira™-C Interbody Device will be compared to historical data based on literature review of fusion rates and patient reported outcomes of traditional PEEK interbody cages.

DESCRIPTION OF SPIRA™-C OPEN MATRIX CERVICAL INTERBODY DEVICE

The Spira™-C Open Matrix Cervical Interbody Device, manufactured by Camber Spine Technologies, was 510(k) cleared by the FDA on October 17, 2017. The Spira™-C device is a 3-D printed titanium alloy cage designed with open spiral supports to allow for a hollow chamber to facilitate the packing of bone graft to optimize fusion. Spira™-C is indicated for use at one or two contiguous levels from C3-C7 for degenerative disc disease (DDD) with up to grade I spondylolisthesis. It is intended to be used with a supplementary FDA-cleared plate fixation system. Spira™-C must be used with autograft or cancellous or cortico-cancellous allograft.

METHODOLOGY

Study Design

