Radiographic assessments will be performed at all postoperative visits; fusion status will be measured using dynamic (flexion and extension) X-rays and CT scan at 12 months. Fusion status at 12-months will be evaluated by an independent spine surgeon. Radiographs, including a cervical spine CT at 12-months, will also be utilized to assess for device-related complications, including implant failure. Any clinically significant complications related to the device will be recorded as an adverse event. Specifically, subsidence, migration, and loosening of the device that result in non-union or pseudoarthrosis and/or clinically significant neurological symptomology will be considered a device failure and reported as an adverse event. Also, any incidental findings on the CT scan will be discussed with patient and a referral to primary care physician will be made for further evaluation if necessary.

Data collected from subjects treated with the Spira™-C Interbody Device will be compared to historical data based on literature review of PEEK cage fusion rates and patient reported outcomes.

This study design reflects the current standard of care for cervical degenerative disc disease and spinal stenosis with symptoms of radiculopathy or myelopathy. Anterior cervical discectomy and fusion using an interbody device with plate and screw fixation is the treatment of choice after conservative therapies (non-surgical, i.e., physical therapy, epidural steroid injections, pain medications) have been exhausted.

Study Population – Inclusion/Exclusion Criteria

Patients scheduled to undergo a primary single-level ACDF surgery between C3-C7 will be approached about potential study participation. If the patient wishes to proceed with study participation, the study coordinator will perform the informed consent process. After the consent process has been completed and study details have been discussed, the subject will be further screened for eligibility and given the subject questionnaires to complete.

Inclusion Criteria

1. ≥ 18 years of age and skeletally mature
2. Able to provide consent
3. Undergoing a primary, single-level ACDF between C3-C7
4. Diagnosis of symptomatic degenerative disc disease
5. Neck pain and/or radicular symptoms with a baseline Visual Analog Scale score of ≥ 4cm (0-10cm scale)
6. Baseline Neck Disability Index score of ≥ 20

7. Attempted at least 6-weeks of conservative non-operative treatment

Exclusion Criteria

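### The EAT-10 endpoint is labelled improvement but is met by any 12-month score below 3, so unchanged or slightly worse subjects can count as improved; the earlier EAT-10 scores enter no endpoint

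*Combined protocol and SAP*

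**What the plan says.** **The endpoint.** Both endpoint lists (Outcomes, Secondary Endpoints; Study Synopsis, Study Endpoints) group four instruments under improvement in patient-reported outcomes. VAS needs a gain of at least 2 points, NDI at least 15 and SF-36 at least 15. The fourth item reads "EAT-10 (score of < 3) from baseline to 12-months".

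**Entry criteria.** Two instruments have a floor at entry: "Neck pain and/or radicular symptoms with a baseline Visual Analog Scale score of ≥ 4cm (0-10cm scale") and "Baseline Neck Disability Index score of ≥ 20". No inclusion or exclusion criterion mentions EAT-10 or dysphagia.

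**Collection and objective.** The Study Schedule of Events collects EAT-10 at baseline, 6 weeks, 3, 6 and 12 months. The synopsis secondary objectives include evaluating "EAT-10 scores postoperatively compared to baseline/preoperative", without naming a visit or a summary measure. The Statistical Analysis section describes no EAT-10 analysis.

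**Adverse events.** The synopsis endpoint is "No occurrence of adverse events related to the device by month 12". The synopsis objective is wider: "To evaluate the occurrence of device-related or procedure related adverse events or complications including subsidence and pseudoarthrosis". The Study Design and Adverse Events sections provide for assessing and recording events related to the device, the procedure or the cervical spine.

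**Use of the results.** They are to be compared with "historical data based on literature review of PEEK cage fusion rates and patient reported outcomes".

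**The concern.** An endpoint called improvement should separate subjects who got better from those who did not. An absolute cut-off does that only if subjects start on the wrong side of it, and nothing here ensures that they do. Dysphagia can also be a consequence of the operation, so many subjects may enter with little or none. For them the rule measures whether they are free of a raised score at 12 months. That is worth knowing, but it is not improvement.

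At stake is how the result is read. A proportion that mixes subjects who were never affected with subjects who recovered cannot be interpreted as change, or set beside an external improvement rate, without the baseline mix.

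The second issue is timing. The endpoint looks at month 12, and no endpoint uses the three earlier post-operative scores. A swallowing problem that appears early and settles could be measured, and even recorded as a procedure-related event, without appearing in any endpoint.

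**Working it through.** **1. The plan's own figure.** The only stated precision is for fusion (Statistical Analysis): 95% Wilson widths of 0.274 at 0.70 and 0.088 at 1.00, with n = 40. The limits are

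[p + z²/2n ± z·√(p(1−p)/n + z²/4n²)] / (1 + z²/n), with z = 1.960.

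- p = 0.70: 0.5457 to 0.8193, width 0.2736.
- p = 1.00: 0.9124 to 1.0000, width 0.0876.

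Both agree after rounding. The same formula is used below. The documents give no baseline EAT-10 distribution and no dysphagia rate, so **every count from here on is hypothetical**.

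**2. The rule applied to single subjects.** Because success is a score below 3, a higher score is taken as worse.

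| Baseline → month 12 | What happened | Counted as |
|---|---|---|
| 0 → 0 | no change | improved |
| 0 → 2 | slightly worse | improved |
| 20 → 3 | much better | not improved |

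A subject with no change can never meet the VAS, NDI or SF-36 rule.

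**3. The rule applied to the group.** Let b be the share entering below 3, q the share of those still below 3 at month 12, and r the share of the others who fall below 3. The reported rate is

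b·q + (1 − b)·r.

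If nobody changes, q = 1 and r = 0, so the rate is b:

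| Entering below 3 | Reported as improved | Wilson 95% interval |
|---|---|---|
| 20/40 | 50% | 35.2% to 64.8% |
| 30/40 | 75% | 59.8% to 85.8% |
| 36/40 | 90% | 76.9% to 96.0% |

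**4. Different outcomes, same reported rate.** Take 30 subjects entering below 3 and 10 entering at 3 or more.

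- (a) Nobody changes: 30 + 0 = 30/40.
- (b) All 10 fall from 20 to 3: 30 + 0 = 30/40.
- (c) Four of the 30 rise to 3 or more, and four of the 10 fall below 3: 26 + 4 = 30/40.

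All three report 75%. Splitting by baseline separates (c) from the other two:

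- (c): 26/30 = 86.7% (70.3% to 94.7%) and 4/10 = 40% (16.8% to 68.7%).
- (a) and (b): 30/30 (88.6% to 100%) and 0/10 (0% to 27.8%).

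The baseline and 12-month scores of the 10 then separate (a) from (b).

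**5. Early dysphagia.** Suppose 6 of the 30 entering below 3 score 3 or more at 6 weeks, are logged as procedure-related, and are below 3 at month 12.

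- EAT-10 endpoint: all 6 count as improved.
- Adverse-event endpoint: none counts, because it takes device-related events only.
- Neurological endpoint: none counts, because it covers motor and sensory deficit.

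A by-visit table would show 6/30 = 20% (9.5% to 37.3%). If 3 of the other 24 were not assessed, it would show 6/27 = 22.2% (10.6% to 40.8%).

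**The case against.** **An absolute state is a legitimate target.** For a possible complication of surgery, being below a threshold at 12 months is a sensible endpoint, and the lack of an entry floor is not a fault in itself; SF-36 has none either. This stands. The defect is that the plan calls the state improvement and pools subjects who could and could not improve.

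**The time phrase might mean below 3 throughout.** If it included baseline, anyone entering with dysphagia could never succeed, which is hard to square with improvement. If it meant every post-operative visit, early dysphagia would count, but a subject at 0 throughout would still be called improved. The month-12 reading fits the list better; the plan should say which is meant.

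**Early dysphagia is already covered.** A reader might infer that it is lost unless someone attributes it to the device. The documents do not support that: EAT-10 is collected at each visit, a synopsis objective compares post-operative scores with baseline, and procedure-related and cervical-spine-related events are recorded. The gap exists at endpoint level only, together with the lack of a defined summary under that objective.

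**The adverse-event wording.** It is tempting to treat the Objective section as contradicting the synopsis. Its sentence says "radiographs will be evaluated for the occurrence of device-related adverse events or complications"; it describes imaging review, which does not assess swallowing, and needs no change. Widening the endpoint to procedure-related events would still miss dysphagia logged as cervical-spine-related and would still depend on reporting.

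**Conclusion.** The concern holds. As written, the rule misclassifies individual subjects in both directions; that follows from the wording and needs no outside figure. At group level, the reported rate equals the share entering below 3 if nobody changes, for example 75% with 30 of 40. At endpoint level, the 6-week, 3-month and 6-month scores are unused, so early dysphagia that resolves and is not attributed to the device enters no endpoint. This assumes the month-12 reading.

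A reader might go further and say that the rate depends mainly on who entered without dysphagia. The documents give no baseline rate to support that. With q = 0.95 and r = 0.30 (both assumed), subjects already below 3 make up 76% of successes at b = 0.5 and 97% at b = 0.9. At b = 0.1 they make up only 0.095 / (0.095 + 0.270) = 26%. Nor do the documents show how the PEEK sources report EAT-10, if they do, so the comparison is uninterpretable without the baseline mix rather than demonstrably biased. They give a score below 3 as success but do not define 3 or more as a diagnosis.

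The consequence is limited: a secondary endpoint in a 40-subject pilot, with no test or success rule for it. Fusion and the sample-size basis are untouched. It should be changed because the correction is cheap and uses data already collected.

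**What to change.** 1. Rename the result *EAT-10 below 3 at 12 months*. Report it separately for subjects below 3 and at 3 or more at baseline. For the second group also show baseline and 12-month scores, descriptively.
2. Under the existing synopsis objective, report at each post-operative visit the number and proportion with EAT-10 of 3 or more among those below 3 at baseline, with the number assessed and Wilson 95% intervals.
3. Leave the Objective section and the device-related adverse-event endpoint as they are. Beside that endpoint, tabulate the procedure-related and cervical-spine-related events already recorded.

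**Cost.** One renamed result, one small table over four visits and one added event tabulation. No new visit, questionnaire or form is needed.

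**Downsides.** The group at 3 or more at baseline may be small, with wide intervals. The dysphagia result will look less favourable. Stray scores add some noise: with 6 true cases among 30 and an assumed chance p of a stray score in each of the other 24, the expected 6-week figure is (6 + 24p)/30, or 20.8% at p = 0.01 and 24.0% at p = 0.05, against a true 20%. That is tolerable for a descriptive table.
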